## Précis

We propose a randomized controlled trial (RCT) to determine the safety and efficacy of aerobic exercise for patients who have interstitial lung disease (ILD) uncomplicated by pulmonary hypertension. Aerobic exercise training (AET) based rehabilitation has become a standard of care for patients with pulmonary diseases such as COPD. In an uncontrolled study, we have observed more efficient cardiorespiratory function, increased physical work capacity, and improved health related quality of life (HRQoL), following AET, in patients who have ILD without pulmonary hypertension. We have also observed in a RCT, similar findings in patients who have pulmonary hypertension complicated by ILD of various etiologies. Serious adverse events resulting from AET were not observed in these studies. Our work to date has established plausibility for the efficacy of AET and its safety for patients with ILD. A RCT is now needed to determine the efficacy of AET as a medically prescribed and supervised intervention in patients who have ILD. Our research team is uniquely qualified to undertake this research and is one of the few teams possessing the experience and background necessary for contributing to this novel, understudied, yet critical field of rehabilitation research.

Subjects will be over the age of 21 years and living within a reasonable travel distance from the greater Washington D.C. area. All tests will be conducted at the NIH Clinical Center and subjects will receive AET or a control regimen of patient education at either Inova Fairfax Hospital or the NIH Clinical Center. The staffs at both sites are well experienced in providing exercise therapy for patients with ILD.

There will be two primary treatment conditions. Patients with ILD will be randomized to either an intervention consisting of AET plus patient education (AET+) or a control condition that includes patient education only (CON). AET will consist of a 10-week regimen of supervised treadmill walking three times a week. The duration of the exercise sessions will progress from 30 minutes to 45 minutes per session over the 10 weeks as tolerated. The intensity of the exercise will be between 70 and 80% of the patient's heart rate reserve. Those randomized to control will not engage in AET. There will, however, be a secondary study: a crossover design in which subjects in the CON group will subsequently complete the AET regimen.

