- 3.2. After AET+, participation in physical activity will be increased over control.
- 3.3. After AET+, overall mood will be increased over control.
- 3.4 After AET, general HRQoL and HRQoL specific to ILD and IPF will all be improved over control.
- 3.5 In the Sub-study on Crossover we hypothesize that AET will result in improvements over baseline in all of the variables of interest including fatigue severity, physical activity, mood state, and HRQoL that are similar to AET+.

**Specific Aim 4:** “One-year Follow Up on Hospitalization, Lung transplant, and Mortality.” In this follow up sub-study, patients will be contacted monthly for one year after completing AET+ regarding frequency and type of exercise subjects have continued; number and nature of hospitalizations; days spent in the hospital; and the severity of their condition causing hospitalization. Subjects’ acceptance onto transplants lists and patient mortality will also be determined. We will examine potential associations among these variables and our variables of interest to determine plausibility of relationships between study outcomes and clinical endpoints.

Two corollary hypotheses will be examined: i) poor clinical outcomes are associated with the severity of cardiorespiratory impairment, and ii) AET-induced improvements in these outcomes are associated with improvements in cardiorespiratory capacity

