- Profile of Mood States (POMS): The Profile of Mood States (POMS) measures present mood state by a list of adjectives. POMS measures six dimensions of affect or mood, including tension-anxiety, depression-dejection, anger-hostility, vigor-activity, fatigue-inertia, and confusion-bewilderment.
- King's Brief Interstitial Lung Disease Health Status Questionnaire (K-BILD): The K-BILD is designed to measure health status in patients with interstitial lung disease through three domains (breathlessness and activities, chest symptoms, and psychological). The questionnaire has 15 items in total.

Randomization: Once the subjects have completed baseline testing they will be randomized to one of the two conditions: AET+ or CON. We will use block randomization to keep groups as equal in number as possible and to avoid early filling of one of the groups. An independent randomizer ([name], P.T., Ph.D., RMD, Epidemiology and Biostatistics Section) who is not affiliated with this study in any other way, will perform randomization of subjects. The AET+ and CON procedures will occur in the Clinical Center at The National Institutes of Health. The education regimen will be conducted at separate times for the AET+ and CON groups to avoid cross contamination.

**Educational Sessions:** The education portion is comprised of 13 separate lectures. Subjects in the AET+ arm will receive 1-2 lectures per week as needed following their exercise session to fulfill the education requirement within 10 weeks. Subjects in the CON arm will receive the 13 lectures within the 10-week education period. Many classes will take more than one class session to cover the material. For example, inhaler use/lung medications will require at least 2 sessions to cover.

The lectures will include the following topics:

- Lung Anatomy/Physiology/Breathing Retraining
- Lung Diseases and Medications Part 1
- Lung Diseases and Medications Part 2
- Oxygen Therapy/Sleep Disorders
- Preventing Infection/Airway Clearance
- Diagnostic Testing
- Advance Care Planning/Energy Conversation
- Emotional/Social Well Being
- Panic Control/Relaxation
- Nutrition/Fall Prevention
- Benefits of Exercise/Disease Management/Community Resources
- Home Recommendations (excluding exercise recommendations)

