## **Participant Inclusion and Exclusion Criteria**

**See Appendix 2 for the Inclusion/Exclusion Checklist that will be used.**

### **Inclusion Criteria**

**ILD Groups:** Subjects in this study will include individuals with ILD who are referred for Pulmonary Rehabilitation. The following list provides more specific inclusion criteria:

- Between age 21-80 years.
- NYHA functional class II or III, will accept NYHA functional class I and IV based on 6 minute walk test results ( $\leq 400$  meters for Class I and  $\geq 50$  meters for Class IV)
- No episodes of syncope or significant chest pain for at least one month.
- No prior Pulmonary Rehabilitation received within the last 6 months and not currently in a maintenance program.
- Physically inactive, no participation in a structured exercise program as defined as more than 30 minutes of exercise 3 or more days a week within the last 6 months.
- Patients may qualify if they have any one of the following conditions:  
Interstitial lung disease, including idiopathic pulmonary fibrosis (IPF), non-specific pulmonary fibrosis (NSIP), sarcoidosis or other form of chronic lung fibrosis based on clinical context via clinic note from primary pulmonologist
- Low to intermediate probability of pulmonary hypertension as determined by tricuspid regurgitation velocity (TRV) at rest on echocardiogram and the presence of additional echocardiographic variables such as right ventricular size and pressure, pattern of blood flow velocity out of the right ventricle, the diameter of the pulmonary artery and an estimate of right atrial pressure. If the patient has had a recent right heart catheterization showing a mean PAP  $< 25$  mmHg, ruling out pulmonary hypertension..

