In order to translate the existing literature's results into predictions of effect size of the 2-way mixed model ANOVA we will use as our primary statistical test, simulations were run in STATA. Simulations were drawn from normal distributions for each of control and exercise groups with equal mean and variance chosen as the average of the mean and variance observed in the control and exercise groups in Holland et al. Specifically, both groups were assumed to have mean 6MWT of 385 m and standard deviation 127 m at baseline in the simulation. The control group was assumed in all samples to show no change between baseline and retest, while different simulations were run for improvement in the exercise group of 25, 30, 35, and 40 m between baseline and retest. We did not simulate differences smaller than 25 m as this is below the MCID. At each level of improvement from treatment we simulated 3000 samples from both control and exercise groups at test-retest correlations of 0.25, 0.30, 0.35, and 0.40.

It was not possible to determine from the previously published ILD literature what level of correlation to expect between test and retest. The preliminary study performed by NIH observed a correlation of 0.840 between pre and post-treatment 6MW distances. We expect a weaker correlation between patients assigned to the CON arm of the proposed study, however, due to the conflicting effects of education and possible decline from the progression of ILD. Additionally, informal study of the plots of pre-post test change in Elia et al. also suggest the range of correlation simulated is conservative. As we are powering on only one of the multiple study aims due to the limitations of prior data and the hierarchy of study goals, we feel it prudent to risk overpowering on this outcome by using overly conservative estimates as it may ensure proper power for the other study aims.

The ranges of improvement in the treatment group and test-retest correlations considered give rise to 16 simulated data sets of 6000 observations each. Each data set was then tested with a 2-way mixed model ANOVA and the effect size recorded. Simulated effect sizes increased across the

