### **Pre-Screening Process in the Inova Pulmonary Rehabilitation Outpatient Department:**

Patient will sign release of record authorization then the patient will be referred to NIH Associate Investigator and Study Coordinator in the Pulmonary Rehabilitation Outpatient Clinic. Then referral records of patients referred for pulmonary rehabilitation for the purposes of prescreening for the study may be reviewed. When a possible patient is identified, the Inova Pulmonary Rehabilitation registrar will contact the patient by telephone to schedule pulmonary rehabilitation. The patient will be informed about the study and will be given the NIH Associate Investigator's contact information if the patient states they are interested. The Inova Fairfax Pulmonary Rehabilitation registrar will state the following to the patient referral after beginning the process of registering the patient for pulmonary rehabilitation:

“You may be eligible for an NIH study examining the benefits of pulmonary rehabilitation for patients with interstitial lung disease. Would you like the contact information for the NIH study coordinator for more information about the study?”

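### Exercise taken up by the education-only arm before the week-10 walk test would go unrecorded, and the shared curriculum includes an exercise-benefits lecture with no fixed place in the schedule.

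*Combined protocol and SAP*

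**What the plan says.** **Control condition.** The Précis states: "Those randomized to control will not engage in AET". Research Objectives likewise describes CON as education only. CON patients take the training regimen after the week-10 test battery.

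**Sizing.** In the Sample Size simulations, "The control group was assumed in all samples to show no change between baseline and retest". Hypothesis 1.1 asks for a gain of at least 30 m over control.

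**Steps against contamination.** Under Randomization: "The education regimen will be conducted at separate times for the AET+ and CON groups to avoid cross contamination". In the lecture list, the item on home recommendations expressly leaves out exercise advice.

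**Lecture content.** The same list, given to both arms, includes "Benefits of Exercise/Disease Management/Community Resources". CON must receive the lectures within the 10-week education period. No order is prescribed.

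**Questions about exercise.** The Overview of the Research Paradigm asks the structured-exercise question at the qualifying evaluation. The next direct enquiry comes after training: under Specific Aim 4, "patients will be contacted monthly for one year after completing AET+ regarding frequency and type of exercise subjects have continued". The overview of the follow-up contacts gives the same timing.

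**Recruitment.** Eligible patients are those referred for pulmonary rehabilitation. Entry requires "No prior Pulmonary Rehabilitation received within the last 6 months and not currently in a maintenance program". In one route the Inova registrar mentions the study "after beginning the process of registering the patient for pulmonary rehabilitation".

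**The concern.** The sponsor treats contamination as a threat worth guarding against: the arms are taught apart and exercise advice is removed from one lecture. Teaching the arms apart does not help with material that CON itself receives. A session pairing the benefits of exercise with community resources could come early in the control period, in patients already referred for rehabilitation, and nothing in the plan would record a programme begun as a result.

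Exercise taken up in CON would move its week-10 walk distance, activity score and quality-of-life scores toward those of the trained arm. The bias is toward no difference. If the primary result were null or small, the trial could not separate a weak training effect from a diluted contrast. The same week-10 value is one of the time points in the crossover analysis, so the within-CON estimate of the training effect would be affected too.

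**Working it through.** **1. What would record outside exercise in CON before the week-10 test**

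| Source in the plan | When | Identifies a programme started in the control period? |
|---|---|---|
| Structured-exercise question (Overview of the Research Paradigm) | Screening | No, too early |
| Monthly contacts (1-year Follow-up; Specific Aim 4) | After training is completed | No, and they concern continued exercise |
| Human Activity Profile (Specific Aim 3) | Before and after the control regimen | Indirectly: a self-reported activity score, itself an efficacy outcome (hypothesis 3.2) |
| AT-time, peak work rate, muscle oxygenation | Before and after the control regimen | Indirectly: a training response might show, its source would not |
| Off-study rule (Monitoring Subjects) | Throughout | Not clearly: it refers to the exclusion criteria, while the exercise and rehabilitation restrictions are inclusion criteria |

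**2. Reproducing the plan's power figures**

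For the group-by-time term with two groups and two times: λ = N × f² × 2 / (1 − r), F test with 1 and N − 2 degrees of freedom, α = 0.05.

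- f = 0.25, r = 0.40, N = 66: λ = 66 × 0.0625 × 2 / 0.60 = 13.75, power 0.955. The plan gives 33 per group for 0.95.
- f = 0.25, r = 0.40, N = 40: λ = 8.33, power 0.803. The plan gives 0.803.

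The convention is the plan's own.

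**3. Illustration of dilution**

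Assume that a share c of CON exercises and gains a fraction g of the AET+ improvement. The contrast, and so the effect size, is multiplied by (1 − c × g). The documents give neither c nor g, so both are assumptions. The range shown is c = 10 to 30%, with g = 1 as the upper end and g = 0.5 as a milder case.

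Inputs: N = 60. f = 0.20 and f = 0.23 are the upper ends of the plan's simulated ranges at 30 m and 35 m (r = 0.40). d = 0.65 and 0.86 are the published t-test effect sizes cited in Sample Size, with 30 per arm.

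| Case | c = 0 | 10%, g = 0.5 | 10%, g = 1 | 20%, g = 1 | 30%, g = 1 |
|---|---|---|---|---|---|
| f = 0.20 | 0.794 | 0.752 | 0.707 | 0.605 | 0.495 |
| f = 0.23 | 0.892 | 0.860 | 0.821 | 0.725 | 0.610 |
| d = 0.65 | 0.697 | 0.652 | 0.606 | 0.508 | 0.410 |
| d = 0.86 | 0.906 | 0.875 | 0.838 | 0.745 | 0.630 |

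Example: f = 0.20, c = 20%, g = 1 gives f = 0.16 and λ = 60 × 0.0256 × 2 / 0.60 = 5.12, power 0.605. In metres, 30 × 0.8 = 24 m, below the smallest improvement simulated (25 m).

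At half gain, 10% uptake costs 0.794 − 0.752 = 0.042, 0.892 − 0.860 = 0.032, 0.697 − 0.652 = 0.045 and 0.906 − 0.875 = 0.031: about 3 to 5 points.

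**4. Limits of the illustration**

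The table shows losses on the plan's convention and does not endorse its absolute power. Taken directly in metres, SD 127 and r = 0.40 give a change SD of 127 × √1.2 = 139 m. A 30 m contrast with 30 per arm then has power of about 0.13, and 27 m about 0.115. That gap in the sizing is a separate matter. The published d values are observed between-group effects, so they may already be net of some control-group activity.

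**The case against.** Several points against the concern have weight.

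- **Earlier evidence.** The Background reports a related randomised trial by the same team in pulmonary hypertension, also comparing training plus education with education only, and found no significant CON improvement. This is the documents' only evidence on how such a control behaves, and it points away from large contamination. It does not settle the matter: the population differs, an identical curriculum is not stated, and a non-significant change is not zero change.
- **The lecture is known only by its title.** A reader might infer that CON is actively urged to exercise. The content is not given, both arms receive the lecture, and general information can coexist with the exclusion of specific advice. What stands is that its timing is uncontrolled. It is the eleventh of twelve printed topics, and if taught in that order it would come late, but the plan does not require that order.
- **Recruitment.** A reader might infer that CON patients attend rehabilitation during the control period, or that the registrar route contradicts the definition of control. The documents support neither. Starting registration is not attending, Inova is itself a training site, recent rehabilitation bars entry, and the coordinator's script and the crossover promise training after the control period.
- **Indirect data exist.** It would go too far to say that contamination would leave no trace. The activity profile and physiological retests could show a shift in CON, but they could not show whether a programme was started.
- **Size.** Full gain from unsupervised exercise is close to a worst case against supervised training three times a week. The half-gain column answers this in part. No rate can be defended from the documents.

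**Conclusion.** The point holds as a gap in control and recording. The plan sizes CON at zero change and guards against contamination, yet leaves an exercise-benefits lecture free to fall early in the control period and does not ask about outside exercise between screening and the end of training. Contamination is possible, not shown.

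The size depends wholly on assumed uptake and gain. On the plan's convention at f = 0.20, the loss runs from about 4 points (10% uptake, half gain) to about 30 points (30% uptake, full gain). The direction, toward no difference, does not depend on those assumptions provided that exercise improves walk distance. The case for acting is that a null or small result could be read more securely at almost no cost, not that the primary contrast is known to be compromised.

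**What to change.** 1. In Educational Sessions, state that this lecture is the last session of the 10-week curriculum in both arms. Content stays equal between arms and the requirement to finish within 10 weeks is kept.
2. At the existing week-10 visit, ask both arms the screening question on structured exercise again, reworded to cover exercise or rehabilitation outside the trial since randomisation.
3. Keep the primary comparison as randomised and report outside-exercise uptake by arm beside it.
4. Ask the sponsor to clarify how the rehabilitation registration begun at Inova relates to the CON period. No particular handling is proposed here.

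Cost: one topic is delivered later and one question is added at a visit that already takes place. No extra visits, staff or patients are needed.

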## **Participant Inclusion and Exclusion Criteria**

**See Appendix 2 for the Inclusion/Exclusion Checklist that will be used.**

### **Inclusion Criteria**

**ILD Groups:** Subjects in this study will include individuals with ILD who are referred for Pulmonary Rehabilitation. The following list provides more specific inclusion criteria:

- Between age 21-80 years.
- NYHA functional class II or III, will accept NYHA functional class I and IV based on 6 minute walk test results ( $\leq 400$  meters for Class I and  $\geq 50$  meters for Class IV)
- No episodes of syncope or significant chest pain for at least one month.
- No prior Pulmonary Rehabilitation received within the last 6 months and not currently in a maintenance program.
- Physically inactive, no participation in a structured exercise program as defined as more than 30 minutes of exercise 3 or more days a week within the last 6 months.
- Patients may qualify if they have any one of the following conditions:  
Interstitial lung disease, including idiopathic pulmonary fibrosis (IPF), non-specific pulmonary fibrosis (NSIP), sarcoidosis or other form of chronic lung fibrosis based on clinical context via clinic note from primary pulmonologist
- Low to intermediate probability of pulmonary hypertension as determined by tricuspid regurgitation velocity (TRV) at rest on echocardiogram and the presence of additional echocardiographic variables such as right ventricular size and pressure, pattern of blood flow velocity out of the right ventricle, the diameter of the pulmonary artery and an estimate of right atrial pressure. If the patient has had a recent right heart catheterization showing a mean PAP  $< 25$  mmHg, ruling out pulmonary hypertension..

### **Exclusion Criteria**

Since the goal is to examine exercise responses and adaptations as affected by ILD, patients will have no other medical conditions that would impair aerobic capacity or the ability to engage in

physical activity. These conditions would include any of those affecting the cardiovascular, pulmonary, metabolic, neurological, or musculoskeletal systems. Specific exclusion criteria are:

- Inability to maintain a resting oxygen saturation  $\geq 90\%$  SpO2, measured by pulse oximetry, on supplemental oxygen.
- Inability to complete a treadmill cardiopulmonary exercise test based on the specified criteria.
- Diagnosis of ischemic heart disease.
- Left ventricular dysfunction with the ejection fraction  $< 50\%$ .
- Acute cor pulmonale.
- Dilated or hypertrophic cardiomyopathy.
- Non-idiopathic cardiomyopathy.
- Significant hepatic or renal dysfunction.
- Metastatic cancer with a life expectancy of less than one year.
- Disabling stroke.
- Active substance abuse.
- Severe psychiatric disease.
- Patients on antiretroviral therapy.
- Uncontrolled diabetes mellitus with a history of DKA.
- Mitochondrial disease.
- Pregnancy.
- Ongoing tobacco use.
- Acceptance onto a lung transplant waiting list.
- No participation in active ILD drug trials prior to enrolling in this study and throughout the duration of their participation in this study. Patients may continue to take any currently prescribed medications throughout the entire protocol. However, any changes to current medications or addition of other medications during the course of the study must be reported within one week to the PI or associate investigator.
- General medical complications that pose a risk to exercise testing or training as determined by the PI (for example, severe peripheral vascular disease).
- Inability to read English.

